#### **Exclusion criteria**

There is no data regarding nifedipine administration in swallowing difficulties. Patients who are unable to swallow and cannot have medications via gastrostomy or equivalent will not be eligible for the nifedipine arm of this study.

Other exclusion criteria are as per the SmPC:

- Known hypersensitivity to nifedipine, other dihydropyridines because of the theoretical risk of cross reactivity or to any of the excipients
- Nursing individuals or those who are or may become pregnant
- Patients with clinically significant aortic stenosis, cardiogenic shock, unstable angina, or during or within one month of a myocardial infarction
- Inflammatory bowel disease, Crohn's disease or with a history of gastrointestinal obstruction, oesophageal obstruction or with decreased diameter of the gastrointestinal lumen
- Hepatic impairment
- Malignant hypertension
- Patients with a Kock pouch (ileostomy after proctocolectomy)
- Concomitant treatment with rifampicin
- Acute porphyria

#### AE reporting requirements

No specific requirements beyond those specified in Section 10.

#### **Contraceptive requirements**

Participants of childbearing potential must use a highly effective method of contraception while taking IMP and it is recommended to continue contraception for 30 days after the last dose of IMP. See Section 5.8 for details.

# **Appendix 4: Ropinirole**

## SmPC

Ropinirole KRKA 2mg prolonged-release tablets, KrKa UK Ltd (formulation-specific SmPCs are available as needed)

## Justification of IMP selection

### Pre-clinical data

Dopamine agonists (DA), as a drug class, have been associated with neuroprotection in multiple pre-clinical models of ALS (bromocriptine in SOD mice; ropinirole in human iPSC MN models (10)), and in other neurodegenerative diseases. Ropinirole is an agonist of the post-synaptic dopamine D2 receptor and is routinely used as a dopamine agonist treatment in patients with Parkinson's disease.

In in vitro model systems ropinirole has been shown to alleviate mitochondrial dysfunction (11,12), to support antioxidant responses (13,14) and exert neurotrophic effects (15). Okano et al, using human ALS iPSC derived model systems showed that ropinirole suppressed oxidative stress, inhibited TDP-43 and FUS aggregation, improved mitochondrial function and reduced neurite retraction and cell death (16). One study showed that ropinirole may affect mitochondrial function by blockade of the mitochondrial permeability transition pore triggered by Ca++ (12). Another study provided evidence that ropinirole increases the synthesis of glutathione (GSH) a major anti-oxidant system in the CNS (14). A drug screen for neuroprotection using a library of FDA approved compounds in an ES-motor neuron TDP-43 model at Oxford University, identified multiple DA agonists, including bromocriptine and pramipexole.

Whether DA agonists exert their potential effect through the DA receptor or through a noncanonical target is unclear, but evidence from an iPSC-based drug screen suggests that it exerts a protective effect by preventing mitochondrial damage, but also that it might have specific effects on reducing aggregation of misfolded TDP-43 (10).

Across multiple pre-clinical models; the related dopamine receptor agonist bromocriptine has shown efficacy in SOD1 mouse models, ropinirole in iPSC models and other DA agonists in ES-MN models. Although the evidence is incomplete, if the main effect is on mitochondrial protection, this is likely to be downstream of pathways at disease initiation.

Dopamine has been shown to promote regeneration of adult motor neurons (17).

#### Phase I, II and II data

To our knowledge, only one clinical trial has been completed with ropinirole in patients with ALS to date – an exploratory study in Japan. The primary outcome was safety (n=13 treated) and the trial demonstrated that ropinirole can be used safely in patients with ALS (18). Further details are provided in Section 4.4.

#### Other available data

Ropinirole has excellent blood-brain barrier penetration and is routinely used in Parkinson's disease. The usual clinical dose of 2-16mg/day will achieve concentrations of approximately 2-16ng/ml in the brain.

#### Adverse events

Ropinirole is in routine clinical use for Parkinson's disease and restless legs syndrome and the side effect profile is well established in these indications. In an exploratory study in ALS, no participants discontinued treatment due to adverse events (AEs) and the incidence of AEs was similar across both groups. The most common ropinirole-related AEs were constipation, nausea, somnolence and headache (18).

## **Dosing in ALS (including titration requirements)**

#### Prolonged-release tablets

Where possible, prolonged-release tablets should be used. Ropinirole HCl extended release in a starting dose of 2mg once per day and building up by 2mg per day at weekly intervals to a dose of 16mg per day. This dosing regime is routinely used and is generally well tolerated in patients with Parkinson's disease.

Participants will be provided with instructions regarding dose titration and advised to contact the study team if they have any questions.

#### Immediate-release tablets

If a participant is unable to use prolonged-release tablets, for example due to swallowing difficulties or PEG insertion, immediate-release tablets may be used (6). The tablets can be crushed and mixed with soft food for patients with swallowing difficulties. The tablets can be crushed and mixed with water for administration via enteral feeding tubes. The conversion chart below will be used to calculate the dose:

Ropinirole prolonged release	Ropinirole immediate release
2mg od	0.75mg TDS (using 0.5mg tablets- can be divided into equal halves)
4mg od	1mg tds
6mg od	2mg tds
8mg od	3mg tds
10mg od	3.5mg tds
12mg od	4mg tds
14mg od	4.5mg tds
16mg od	6mg tds

#### Dose modifications and interruptions in ALS

If a participant experiences undesirable effects that they cannot tolerate, the dose can be reduced to a previously tolerated dose at the discretion of the local investigator.

If treatment is interrupted for one day or more, re-initiation by dose titration should be considered as above at the discretion of the local investigator.

Dose modifications can be done between scheduled visits if required. Further details are provided in the Research Manual and Pharmacy Manual.

## Drug withdrawal

As a precautionary step, due to the risk of dopamine agonist withdrawal syndrome (DAWS), treatment should be discontinued slowly by reducing the daily dose gradually. The recommended schedule is to reduce the dose gradually over the course of one week. An additional dispensing may be required at week 24 to cover the withdrawal period. Further details are included in the Pharmacy Manual and Research Manual.

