## 10.3 Identification and assessment at site

#### Identification

AEs/SAEs which are not exempt (as per Section 10.2) will be recorded in the eCRF from consent until the participant has completed their involvement in the trial, up to week 24.

Participants will be asked about AEs/SAEs at every study visit with open-ended and nonleading verbal questioning. Participants will also be asked if they have been admitted to hospital or had any accidents. AE data may also be identified via information in the medical records.

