#### **10.4 Recording and reporting**

AEs and ARs will be recorded from the time of consent for trial entry until the participant has completed their involvement in the trial, up to week 24.

AEs and ARs except those exempt as per section 10.2 will be recorded on the adverse event report form, within the study database, including those that fulfil the criteria for being serious (see section 10.1). Sites are asked to enter all available information onto the study database as soon as possible after the site becomes aware of the event.

Out of range lab values will only be recorded as an AE if they are considered clinically significant and require intervention to treat.

SAEs, SARs and SUSARs will require more detailed information to be recorded. In such cases, the event must also be reported to the Sheffield CTRU within 24 hours of the site becoming aware of the event. The CTRU will notify the Sponsor of each of these events in accordance with the Agreement between Sheffield Teaching Hospitals and University of Sheffield.

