## **10.5 SAE notification procedure**

Site staff must notify CTRU of all SAEs within 24 hours of becoming aware of the event, with the exception of the events listed in Section 10.2. All SAEs must be reported on the Serious Adverse Event (SAE) reporting form and sent to CTRU by email: [contact] within the reporting timelines.

The SAE form must be completed by the investigator (a clinician named on the delegation log who is responsible for the participant's care). In the absence of the investigator the form will be completed by a member of the study team and emailed as appropriate. The responsible investigator will subsequently check the SAE form, make changes as appropriate, sign and re-send the form to CTRU as soon as possible.

Receipt of the initial report should be confirmed by CTRU within one working day. The site research team should contact the study team at CTRU if confirmation of receipt is not received within one working day.

Concomitant medications are recorded throughout the study and will not be collected on SAE forms as standard. However for any event classified as a SAR or SUSAR CTRU may request additional information on concomitant treatments to facilitate onward reporting.

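### Ropinirole completers taper for a week after week 24, but adverse event recording and scheduled questioning stop at week 24

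*Protocol*

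**What the plan says.** Appendix 4 (Ropinirole, Drug withdrawal) asks for gradual dose reduction as a precaution against dopamine agonist withdrawal syndrome. On timing it states: "The recommended schedule is to reduce the dose gradually over the course of one week". On supply it states: "An additional dispensing may be required at week 24 to cover the withdrawal period". It then refers the reader elsewhere: "Further details are included in the Pharmacy Manual and Research Manual". The same appendix adds no monitoring beyond Section 9 and no adverse event reporting beyond Section 10.

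Section 10.3 has non-exempt AEs and SAEs entered in the eCRF from consent "until the participant has completed their involvement in the trial, up to week 24". Section 10.4 gives the same window for AEs and adverse reactions: from consent "for trial entry until the participant has completed their involvement in the trial, up to week 24". Section 10.3 says how events are found: "Participants will be asked about AEs/SAEs at every study visit", with medical records as a further source.

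In the assessment schedule (Section 9.1, Table 2), week 24 is the last scheduled participant visit. Section 9.2 adds a month 12 review of survival status, preferably made without contacting the participant.

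**The concern.** The taper is the one period for which the protocol itself names a withdrawal risk for this drug. For participants who take ropinirole to week 24, it begins when safety data collection ends. A site that follows the protocol exactly would supply the tapering doses and then neither ask about nor enter in the eCRF what happens while they are taken.

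Safety and tolerability is the first secondary objective, and the platform exists to decide which drugs go on to Phase III. Section 11.1 allows better safety to count in favour of a lower-ranked drug. How patients with ALS tolerate coming off ropinirole is useful for that decision, and this is the trial's chance to observe it.

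**Working it through.** No power or sample size figure of the plan is at issue. The check compares timelines and then counts the participants concerned.

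**Timeline for a completer**

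- Week 24 = 24 × 7 = day 168. Recording ends here (Sections 10.3 and 10.4).
- End of the recommended taper = 168 + 7 = day 175 (Appendix 4).
- Dosing outside the window = 175 − 168 = up to 7 days, plus any time after the last dose in which a reaction could appear.
- With the ±1 week visit window in Table 2, the final visit falls at week 23 to 25 and the taper ends at about week 24 to 26. An early visit can put the taper nominally inside week 24, but in every case it follows the last visit at which events are asked about.
- The next scheduled item is the month 12 survival review.

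**Does anything else in the protocol close the gap?**

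| Place | What it provides | Covers new taper events? |
|---|---|---|
| Section 9.1, Table 2 | Dispensing last at week 18; accountability last at week 24 or early discontinuation | No; not extended for the taper |
| Section 9.3 | Unscheduled calls at the site's discretion | Only if the site chooses |
| Section 10.5, Follow up | Continued follow-up of SAEs already reported | No |
| Sections 10.4 and 10.5 | SAE notification within 24 hours of awareness | Serious events only, if the site learns of them |
| Appendix 4, monitoring and AE reporting | Nothing beyond Sections 9 and 10 | No |

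The adverse event rows of Table 2 are merged cells whose right-hand limit cannot be read in the text available, so I do not rely on them. Sections 10.3 and 10.4 state the limit in words.

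**Who is affected**

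Participants who stop early but stay in follow-up have scheduled visits to week 24 (Section 9.10). Their tapers fall inside the window unless they stop in the last 7 days. The gap therefore concerns completers.

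*Arm retained to 80 patients at 24 weeks (Section 11.1).* The protocol gives no early-stopping rate, so I assume 10% to 30%:

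- 80 × 0.70 = 56
- 80 × 0.90 = 72

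*Arm dropped for futility.* Treatment then stops (Section 2.4), so only those who reach week 24 first are affected. I take the minimum triggers in Section 11.2 as the counts and 10% early stopping for the upper end. The lower end is 0.

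| Dropped after | Treatment stopped within 6 weeks of the trigger (only those already at 18 weeks can reach week 24) | Treatment stopped within 12 weeks (only those already at 12 weeks can reach week 24) |
|---|---|---|
| Futility analysis 1 (about 28 randomised) | 16 × 0.90 = 14.4, so 0 to 14 | 23 × 0.90 = 20.7, so 0 to 20 |
| Futility analysis 2 (about 35 randomised) | 20 × 0.90 = 18.0, so 0 to 18 | 29 × 0.90 = 26.1, so 0 to 26 |

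The 6 and 12 week delays are also assumptions.

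**The case against.** The strongest reply is that the gap is small and partly rests on documents not shown. Appendix 4 calls the taper a precaution, makes the schedule a recommendation and the extra supply a possibility, and leaves details to the Pharmacy and Research Manuals, which may include a follow-up call. This stands as a limit. However, a call in a manual would not change the recording window in Sections 10.3 and 10.4. Sections 9.6 and 10 also name the IMP appendix as the place for drug-specific monitoring and reporting, and Appendix 4 adds none. The conditional wording applies to the dispensing; it does not move the withdrawal period to before week 24.

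Second, serious events are largely protected. Section 10.4 says that "the event must also be reported to the Sheffield CTRU within 24 hours of the site becoming aware of the event", and Section 10.5 that "Site staff must notify CTRU of all SAEs within 24 hours of becoming aware of the event", the latter without an end date. This stands too. What is lost is mainly non-serious events and active questioning.

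Third, participants stay under their ALS clinic, carry a contact card while in the trial and may be telephoned. These routes help to protect the patient but do not put a non-serious taper event into the eCRF.

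Fourth, no trial conclusion is shown to change. Ropinirole is licensed with a known side-effect profile, the AE outcome as defined is not biased, and the NFL analysis is untouched. All of this is correct, and it limits the weight of the point.

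Finally, the counts depend on assumed rates. The dropped-arm figures treat minimum triggers as the actual numbers, so they are not strict upper bounds. The retained-arm figure would rise if the arm became the reference drug and kept recruiting, or if its target were increased.

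**Conclusion.** The concern holds. As written, the protocol directs dosing after week 24 for ropinirole completers while ending AE recording at week 24, and it schedules no later contact that asks about new events. The uncovered time is up to 7 days of dosing per completer plus the period just after the last dose. About 56 to 72 participants are affected if the arm reaches 80, and fewer if it is dropped, under the assumptions shown. The number of events missed cannot be stated.

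The AE outcome is correctly analysed for the window it defines; the definition leaves out the taper. This is a change that should be made for completeness of the safety data, not a threat to the primary analysis. Confidence is medium, mainly because the two manuals are not available.

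**What to change.** Amend Sections 10.3 and 10.4 so that AE and SAE recording runs to week 24 or to the end of any protocol-directed taper, whichever is later. In Appendix 4, add one telephone or video contact shortly after the last tapered dose, and enter it in Table 2. Apply the same rule to any other drug whose taper runs past the week 24 visit; the 3-day salbutamol taper in Appendix 5 is a candidate.

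Section 11.1 compares adverse events between arms by Poisson regression. Keep that comparison to events up to week 24 and report taper-period events separately by arm, so that tapering arms do not get a longer counting window.

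The cost is a protocol wording change and one extra remote contact per tapering completer.

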### **Monitoring requirements for ALS**

No specific requirements beyond those specified in Section 9.

## **Exclusion criteria**

Presence or history of any psychotic disorder is an exclusion for the ropinirole arm in this study.

Other exclusion criteria are as per SmPC:

- Hypersensitivity to the active substance or to any of the excipients
- Severe renal impairment (creatinine clearance\* <30ml/min) without regular haemodialysis
- Hepatic impairment

\* eGFR will be used to assess renal function in EXPERTS-ALS

#### AE reporting requirements

No specific requirements beyond those specified in Section 10.

#### **Contraceptive requirements**

Participants of childbearing potential must use a highly effective method of contraception while taking IMP and it is recommended to continue contraception for 30 days after the last dose of IMP. See Section 5.8 for details.

# Appendix 5: Salbutamol (also known as albuterol)

## SmPC

Ventolin Syrup, Salbutamol Sulphate, GlaxoSmithKlineUK

## Justification of IMP selection

The rationale for use of  $\beta$ 2 receptor agonists in ALS is largely based on positive effects of this drug class in other muscle-wasting, neuromuscular, and neurodegenerative diseases. Stimulation of  $\beta$ 2-adrenoceptors activates many signalling pathways in different tissues and cell types that can maintain or enhance cell viability under conditions of physical stress, many of which may be relevant to ALS (see figure in appendix). In vivo,  $\beta$ 2 agonists have been shown to have an anabolic effect on muscle fibres and increase muscle strength and mass, improve neuromuscular transmission, reverse muscle wasting, and delay the onset of motor deficits in a range of animal models of muscle degeneration. Animal studies have also indicated they may exert neuroprotective effects and promote neural repair following different insults, although the precise mechanism is not clear.

The clinical efficacy of  $\beta$ 2-agonists has been tested in a variety of neuromuscular diseases of different types (e.g., those with a primary neurologic pathology, as in ALS, those characterised by degeneration and dysfunction of the NMJ, and those with a primary myopathology), with a range of effects reported, including improved muscle strength and mass (19). Some positive clinical results of  $\beta$ 2-agonists on motor function and immunologic responses have been reported in multiple sclerosis (20,21) and a press release from a Phase II trial in Parkinson's disease and mild cognitive impairment claimed rapid improvements in cognition and mood (22).

BBB penetrance: Studies on rats found salbutamol reached brain concentrations amounting to ~5% of plasma concentrations. In structures outside the BBB (pineal and pituitary glands found in concentrations >100x those in whole brain (23).

#### Preclinical

Very few preclinical studies have investigated the effects of  $\beta$ 2-agonists in ALS models. Those identified are shown below. Overall, evidence for a beneficial effect is limited and appears to vary with the model used, assay and outcome measure.

Linares et al. (2023) (24) performed a phenotypic screen of a small molecule library of approved drugs for the ability to increase ALS/FTD induced motor neuron (iMN) survival. iMNs carrying C9orf72 expansions were first used. Candidates found to improve survival were then tested on a wider panel of C9orf72 lines (3 independent lines) and a sporadic ALS (sALS) iMN panel (8 lines in total). This screen included several β2-agonists (see below). Only bambuterol was found to be effective in C9orf72 iMNs and sALS lines (note: other drugs not tested in sALS lines).

Drug	Effect on C9ORF72 iMNs	Effect on sALS iMNs
Albuterol	Improved survival, but not significantly.	N/A
Bambuterol	Significantly improved survival	Significantly improved survival of 6/8 iMN lines
Terbutaline	Did not affect survival	N/A
Clenbuterol	Did not affect survival	N/A
Fenoterol	Did not affect survival	N/A
Ritodrine	Did not affect survival	N/A

#### Clinical data

Salbutamol (Albuterol)

- Brooks et al. (2014) (25) performed a retrospective clinical audit of systemic albuterol use in non-invasive ventilation-supported ALS patients and found it was well-tolerated. ALSFRS-R respiratory-, but not bulbar-sub-score was significantly decreased in treated patients. Vital capacity remained unchanged at 3 months but declined at 6 months.
- Brooks et al. (2000) (26) evaluated effect on neck flexion (NF) strength in ALS patients (unclear RoA/dose). Treated patients showed delayed decline in NF due to sustained improvement in neck muscle strength.
- A Phase II monocentric, randomised, controlled, pilot study (not yet recruiting) is planned to evaluate effect of salbutamol on walking capacity in 36 ambulatory ALS patients (NCT05860244) (27). The study will also measure target engagement, as well as safety and tolerability. Exploratory objectives include fatigue scales, muscle strength, respiratory function, motor unit count, muscle/spinal MRI parameters and blood biomarkers of muscle damage (CPK, LDH and creatinine serum levels).

#### **Adverse events**

Adverse events are not anticipated to be different from a non ALS population. Precautions are therefore as per SmPC.

Owing to the hypokalaemic effect of beta-agonists, concurrent administration of serum potassium depleting agents known to exacerbate the risk of hypokalaemia, such as diuretics, digoxin, methyl xanthines and corticosteroids, should be administered cautiously after careful evaluation of the benefits and risks with special regard to the increased risk of cardiac arrhythmias arising as a result of hypokalaemia.

## **Dosing in ALS (including titration requirements)**

Salbutamol 2mg tds then one week later increase to 4mg tds.

## Dose modifications and interruptions in ALS

If experiencing tolerability issues, dose can be reduced to 2mg tds and further reduced to 1mg tds if required. If 1mg tds is not tolerated then withdraw salbutamol.

If dose is interrupted, re-introduction should involve retitration.

